### **10.3. Treatment of Missing and Spurious Data**

See general definitions in chapter 5.4.

### **10.4. Exclusion of Particular Information**

See general definitions in chapter 5.5. No data are excluded from the specified analysis set and variables.

### **10.5. Descriptive Analyses**

For specification "Notes = descriptive", see general definitions in chapter 5.1.

### **10.6. Hypotheses & Statistical Tests**

There are no pre-defined statistical hypotheses.

## 11. ADE and DD Endpoints – PHD & follow-up

### CIP chapter 7.2.2. Endpoints

*In this study the number of adverse device effects and device deficiencies (DD) that occur in patients, users or other persons will be evaluated ...*

- *Number of adverse device Effects / device deficiencies per number of implantations*
- *Number of adverse device Effects / device deficiencies and per number of follow-up cases*

*ADEs will be adjudicated by an internal adjudication board, whereby the seriousness and device relatedness will be re-examined. If any amply documented external physical influence (e.g. accident, general power blackout) or medical AE caused the ADE, it does not contribute to this endpoint.*

ADEs and device deficiencies are adjudicated by an internal adjudication board.

### 11.1. Analysis Set and Data Selection

All analyses are performed for patients in the PHD & follow-up analysis set using a specific data selection after implantation.

All analyses from chapter 10 ADE and DD Endpoints - Implantation are repeated for these data.

---

 analysis set PHD FUP SAR = Yes and PRUCASE = PHD / Follow-up

## 12. Implantation & PSA

### CIP chapter 7.5 Further data of interest

During implantation and follow-ups additional data on safety, performance and usability of the Renamic Neo system and accessories will be collected.

- Use and assessment of PSA functionality (sensing, pacing and impedance tests)...

### 12.1. Analysis Set

All analyses are performed for patients in the implantation analysis set.

### 12.2. Variables

#### Used Programmer Features: Pacing System Analyzer (PSA)

Data file, identifier patient display id full	Notes	Variable name	Variable label	Variable Level	Nominal values
implantation_psa	descriptive	PRIMPASA	Was the PSA functionality used during implantation	nominal	 Yes  No
	descriptive with "not used" handled as missing	QSPLRAS	Polarity selection and documentation	nominal	 used successfully  used, but not successfully  not used
	descriptive#	QSPLRSPR	NEW: Polarity: Did you notice any problem	nominal	 Yes, with Adverse Event  Yes, without Adverse Event  No problem detected
	descriptive with "not used" handled as missing	QSSAAS	Sensing amplitude	nominal	 used successfully  used, but not successfully  not used
	descriptive#	QSSAPRB	NEW: Sensing amplitude: Did you notice any problem	nominal	 Yes, with Adverse Event  Yes, without Adverse Event  No problem detected
	descriptive with "not used" handled as missing	QSPTAS	Pacing threshold	nominal	 used successfully  used, but not successfully  not used
	descriptive#	QSPRPRB	NEW: Pacing threshold: Did you notice any problem	nominal	 Yes, with Adverse Event  Yes, without Adverse Event  No problem detected
	descriptive with "not used" handled as missing	QSPITAS	Impedance test	nominal	 used successfully  used, but not successfully  not used
	descriptive#	QSPITPRB	NEW: Impedance test: Did you notice any problem	nominal	 Yes, with Adverse Event  Yes, without Adverse Event  No problem detected
	descriptive with "not used" handled as missing	QSPNSAS	Phrenic Nerve Stimulation (PNS) test and documentation	nominal	 used successfully  used, but not successfully  not used
	descriptive#	QSPNSPRB	NEW: PNS test: Did you notice any problem	nominal	 Yes, with Adverse Event  Yes, without Adverse Event  No problem detected
	descriptive with "not used" handled as missing	QSBSAS	Burst stimulation if performed in routine care	nominal	 used successfully  used, but not successfully  not used
	descriptive#	QSBSPRB	NEW: Burst stimulation: Did you notice any problem	nominal	 Yes, with Adverse Event  Yes, without Adverse Event  No problem detected

# If preceding variable = "used successfully" then impute missing data with "used successfully".

 analysis set imp SAR = Yes

Data file, identifier patient display id full	Notes	Variable name	Variable label	Variable Level	Nominal values
implantation psa	case listing for QSPLRAS = used, but not successfully OR QSPLRSPR = Yes, with Adverse Event OR QSPLRSPR = Yes, without Adverse Event including programmer serial number DIPRGSNR (see chapter15.1)	COPLRSPR	NEW: Polarity amplitude: Please specify reason for unsuccessful use	text	...
	case listing for QSSAAS = used, but not successfully OR QSSAPRB = Yes, with Adverse Event OR QSSAPRB = Yes, without Adverse Event including programmer serial number DIPRGSNR (see chapter15.1)	COSAAS	NEW: Sensing amplitude: Please specify reason for unsuccessful use	text	...
	case listing for QSPTAS = used, but not successfully OR QSPRPRB = Yes, with Adverse Event OR QSPRPRB = Yes, without Adverse Event including programmer serial number DIPRGSNR (see chapter15.1)	COPTAS	NEW: Pacing threshold: Please specify reason for unsuccessful use	text	...
	case listing for QSPITAS = used, but not successfully OR QSPITPRB = Yes, with Adverse Event OR QSPITPRB = Yes, without Adverse Event including programmer serial number DIPRGSNR (see chapter15.1)	COPITAS	NEW: Impedance test: Please specify reason for unsuccessful use	text	...
	case listing for QSPNSAS = used, but not successfully OR QSPNSPRB = Yes, with Adverse Event OR QSPNSPRB = Yes, without Adverse Event including programmer serial number DIPRGSNR (see chapter15.1)	COPNSAS	NEW: PNS test: Please specify reason for unsuccessful use	text	...
	case listing for QSBSAS= used, but not successfully OR QSBSPRB = Yes, with Adverse Event OR QSBSPRB = Yes, without Adverse Event including programmer serial number DIPRGSNR (see chapter15.1)	COBSAS	NEW: Burst stimulation: Please specify reason for unsuccessful use	text	...

Used Measurement Mode: Pacing System Analyzer (PSA)

Data file, identifier patient display id full	Notes	Variable name	Variable label	Variable Level	Nominal values
implantation psa	descriptive	DUSCHM	Single chamber mode (Single chamber devices or if leads of dual and triple chamber devices are measured consecutively in single-chamber mode, e.g. VVI)	nominal	o Yes o No
	descriptive	DUDCHM	Dual chamber mode (e.g. VDD RV)	nominal	o Yes o No
	descriptive	DUTCHM	Triple chamber mode (e.g. DDI BiV)	nominal	o Yes o No
	descriptive	DURFSE	Was radio frequency (RF) electrosurgical equipment used while the PSA was connected to the pacing lead(s)	nominal	o Yes o No

Data file, identifier patient display id full	Notes	Variable name	Variable label	Variable Level	Nominal values
implantation psa	case listing for DURFSE = Yes	DURFSETY	Please specify type of RF surgical equipment used	text	...

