	descriptive with "not used" handled as missing	QSPTAS	Pacing threshold	nominal	 used successfully  used, but not successfully  not used
	descriptive#	QSPRPRB	Did you notice any problem* (see definition above) with usage of pacing threshold	nominal	 Yes, with Adverse Event  Yes, without Adverse Event  No problem detected
	descriptive with "not used" handled as missing	QSPITAS	Impedance test	nominal	 used successfully  used, but not successfully  not used
	descriptive#	QSPITPRB	Did you notice any problem* (see definition above) with usage of impedance test	nominal	 Yes, with Adverse Event  Yes, without Adverse Event  No problem detected
	descriptive with "not used" OR VectorOpt not available ..." handled as missing	QSDFPAS	LV Pacing threshold and PNS measurement for different polarities	nominal	 used successfully  used, but not successfully  not used  VectorOpt not available for CRT implant
	descriptive#	QSDFPPRB	Did you notice any problem* (see definition above) with usage of LV Vector Opt function	nominal	 Yes, with Adverse Event  Yes, without Adverse Event  No problem detected
	descriptive with "not done" handled as missing	QSPRGAS	Programming of the implant	nominal	 device successfully programmed  device not successfully programmed  not done
	descriptive#	QSPRGPRB	Did you notice any problem* (see definition above) with usage of programming of the implant function	nominal	 Yes, with Adverse Event  Yes, without Adverse Event  No problem detected
	descriptive with "not used" handled as missing	QSDFTAS	DFT (Defibrillation Threshold Testing) if performed in routine care	nominal	 used successfully  used, but not successfully  not used
	descriptive#	QSDFTPRB	Did you notice any problem* (see definition above) with usage of DFT	nominal	 Yes, with Adverse Event  Yes, without Adverse Event  No problem detected

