# If preceding variable = "used successfully" or "device successfully programmed" then impute missing data with " Used successfully".

Data file, identifier patient display id full & autom SVTYP	Notes	Variable name	Variable label	Variable level	Nominal values
general assessments (see Analysis Set and Data Selection)	case listing for QSPGHAS = used, but not successfully OR QSPGHPRB = Yes, with Adverse Event OR QSPGHPRB = Yes, without Adverse Event including programmer serial number DIPRGSNR (see chapter15.1)	COPGHAS	Please specify reason for unsuccessful use of programmer head telemetry	text	...
	case listing for QSRFTAS = used, but not successfully OR QSRFTPRB = Yes, with Adverse Event OR QSRFTPRB = Yes, without Adverse Event including programmer serial number DIPRGSNR (see chapter15.1)	CORFTAS	Please specify reason for unsuccessful use of RF telemetry for implant interrogation	text	...
	case listing for QSSAAS = used, but not successfully OR QSSAPRB = Yes, with Adverse Event OR QSSAPRB = Yes, without Adverse Event including programmer serial number DIPRGSNR (see chapter15.1)	COSAAS	Please specify reason for unsuccessful use of sensing amplitude	text	...
	case listing for QSPTAS = used, but not successfully OR QSPRPRB = Yes, with Adverse Event OR QSPRPRB = Yes, without Adverse Event including programmer serial number DIPRGSNR (see chapter15.1)	COPTAS	Please specify reason for unsuccessful use of pacing threshold	text	...
	case listing for QSPITAS = used, but not successfully OR QSPITPRB = Yes, with Adverse Event OR QSPITPRB = Yes, without Adverse Event including programmer serial number DIPRGSNR (see chapter15.1)	COPITAS	Please specify reason for unsuccessful use of impedance test	text	...
	case listing for QSDFPAS = used, but not successfully OR QSDFPPRB = Yes, with Adverse Event OR QSDFPPRB = Yes, without Adverse Event including programmer serial number DIPRGSNR (see chapter15.1)	CODFPAS	Please specify reason for unsuccessful use of LV Vector Opt function	text	...
	case listing for QSPRGAS = used, but not successfully OR QSPRGPRB = Yes, with Adverse Event OR QSPRGPRB = Yes, without Adverse Event including programmer serial number DIPRGSNR (see chapter15.1)	COPRGAS	Please specify reason for unsuccessful programming of the implant	text	...

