# If preceding variable = "Yes" then impute missing data with "Used successfully".

Data file, identifier patient display id full & autom SVTYP	Notes	Variable name	Variable label	Variable level	Nominal values
general assessments (see Analysis Set and Data Selection)	case listing for QSCNNAS = No OR QSCNNPRB = Yes	COCNNAS	NEW: Connectivity: Please specify reason for unsuccessful use	text	...
	case listing for PRDEXPAS = No OR QSDEXPPR = Yes	CODEXPAS	NEW: Data export: Please specify reason for unsuccessful use	text	...
	case listing for DUOTH = Yes	COOTH	NEW: Data export: Please specify Other	text	...

Used Programmer Features: Printing

Data file, identifier patient display id full & autom SVTYP	Notes	Variable name	Variable label	Variable level	Nominal values
general assessments (see Analysis Set and Data Selection)	decriptive	PRPRNT	Was printing performed	nominal	o Yes o No
		DULAN02	NEW: Printing LAN	nominal	o Yes o No
		DUWLAN02	NEW: Printing WLAN	nominal	o Yes o No
		DUUSB02	NEW: Printing USB	nominal	o Yes o No
		QSPRNTAS	Was printing successful		o Yes o No
		QSPRNTPR #	NEW: Printing: Did you notice any problem* (see definition above)	nominal	o Yes o No problem detected
		DUPRNTTY	Please specify which printer type was used	nominal	...

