# If preceding variable = "Yes" then impute missing data with "Used successfully".

Data file, identifier patient display id full & autom SVTYP	Notes	Variable name	Variable label	Variable level	Nominal values
general assessments (see Analysis Set and Data Selection)	case listing for QSPRNTAS = No OR QSPRNTPR = Yes	CODEXPAS	NEW: Printing: Please specify reason for unsuccessful use	text	...

Used Programmer Features: Battery

Data file, identifier patient display id full & autom SVTYP	Notes	Variable name	Variable label	Variable level	Nominal values
general assessments (see Analysis Set and Data Selection)	descriptive with "not used" handled as missing	PRPRGB	Was the programmer used with the battery as power supply (without power cable, usage is optional)	nominal	o used successfully o used, but not successfully o not used
	descriptive, if PRPRGB = "successfully used" then impute missing QSPRGBPR with "No problem detected".#	QSPRGBPR	NEW: battery: Did you notice any problem* (see definition above)	nominal	o Yes, with Adverse Event o Yes, without Adverse Event o No problem detected

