# If preceding variable = "Used successfullyyes" then impute missing data with "Used successfully".

Data file, identifier patient display id full & autom SVTYP	Notes	Variable name	Variable label	Variable level	Nominal values
general assessments (see Analysis Set and Data Selection)	case listing for PRPRGB= used, but not successfully OR QSPRGBPR = Yes, with Adverse Event OR QSPRGBPR = Yes, without Adverse Event including programmer serial number DIPRGSNR (see chapter15.1)	COPRGB	NEW: Battery: Please specify reason for unsuccessful use	text	...

Assessment of Programmer Features

Data file, identifier patient display id full & autom SVTYP	Notes	Variable name	Variable label	Variable level	Nominal values
general assessments (see Analysis Set and Data Selection)	descriptive	QSCNSAS	Are the connectivity settings (e.g. WLAN, LAN, printer) easy / difficult to find	nominal	 Very easy  Easy  Adequate  Somewhat difficult  Very difficult
		QSPSAPAS	Are the PSA parameters (e.g. amplitude, basic rate, mode) easy / difficult to find	nominal	 Very easy  Easy  Adequate  Somewhat difficult  Very difficult
		QSPGPV	Is the range of programmable variables for connectivity settings (e.g. WLAN, LAN, printer) sufficient	nominal	 Yes  No
		QSRGPSA	Is the range of the PSA parameters (e.g. amplitude, basic rate, mode) sufficient for the treatment of the patient	nominal	 Yes  No
		QSANYPRB (Note: No missing data need to be imputed)	Did you notice any problems* (including IEGM and ECG recording) which are not mentioned yet relating to the device hardware or software	nominal	 Yes, with Adverse Event  Yes, without Adverse Event  No problem detected

Data file, identifier patient display id full & autom SVTYP	Notes	Variable name	Variable label	Variable level	Nominal values
general assessments (see Analysis Set and Data Selection)	case listing for QSCNSAS = Somewhat difficult OR QSCNSAS = Very difficult including programmer serial number DIPRGSNR (see chapter15.1)	COCNSAS	NEW: Data export: Please specify Somewhat difficult / Very difficult	text	...

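### The SAP fills blank problem items with an answer those items do not have, gives the battery item two fill rules that disagree, and lists failed programming on a value that cannot occur (minor)

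*SAP*

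**What the plan says.** **Fill rules.** In SAP 12.2 (pacing system analyzer, PSA) and 13.1 (implant features, data export, printing, battery), each usage item is followed by an item asking whether any problem was noticed. Blanks in the second item are filled after successful use:

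- PSA items, 12.2: "If preceding variable = 'used successfully' then impute missing data with 'used successfully".
- Implant items, 13.1: "If preceding variable = 'used successfully' or 'device successfully programmed' then impute missing data with" *Used successfully*.
- Connectivity and data export, and again printing, 13.1: "If preceding variable = 'Yes' then impute missing data with 'Used successfully".
- Battery, 13.1, Notes cell: "if PRPRGB = 'successfully used' then impute missing QSPRGBPR with 'No problem detected".
- Battery, 13.1, # note: "then impute missing data with 'Used successfully", with the trigger printed as *Used successfullyyes*.

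**Permitted answers.** The PSA, implant and battery problem items take two kinds of Yes (with or without an adverse event) or "No problem detected". The connectivity, export and printing problem items take Yes or that same no-problem answer.

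**Programming listing.** The failure value of QSPRGAS (programming of the implant) is "device not successfully programmed". The listing of COPRGAS, the reason text, is specified as "case listing for QSPRGAS = used, but not successfully OR QSPRGPRB = Yes, with Adverse Event", with the other kind of Yes as a further alternative.

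**Reach.** SAP 14.1 repeats the chapter 13 analyses for PHD and follow-up. SAP 1.2 says that original database values are reported unless a new nominal value is defined and marked NEW.

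**The concern.** A SAP of this kind is close to a programming specification: each row names a variable, its values and the rule to apply. Here some rules name values that the variable does not have.

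If the # notes are run as written, the frequency tables for the problem items contain a row that is not an answer to the question, and the no-problem row is too small by the number of filled blanks. For the battery item the two instructions disagree. For programming, the listing meant to explain failures cannot be triggered by a failure alone. Protocol 7.5 names success of adequate programming as data of interest, so the reasons for failure are what a reader of the report would look for.

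What is at stake is the descriptive performance and usability tables and one case listing. The endpoints are not.

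**Working it through.** The plan states no figure on this point, so there is none to reproduce. The check compares each fill value and trigger with the item's own value list, and then sizes the effect.

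**Step 1. Items carrying the # rule at implantation.**

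| Block | Problem items | Count |
|---|---|---|
| PSA (12.2) | QSPLRSPR, QSSAPRB, QSPRPRB, QSPITPRB, QSPNSPRB, QSBSPRB | 6 |
| Implant (13.1) | QSPGHPRB, QSRFTPRB, QSSAPRB, QSPRPRB, QSPITPRB, QSDFPPRB, QSPRGPRB, QSDFTPRB | 8 |
| Connectivity and export (13.1) | QSCNNPRB, QSDEXPPR | 2 |
| Printing (13.1) | QSPRNTPR | 1 |
| Battery (13.1) | QSPRGBPR | 1 |

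Total: 6 + 8 + 2 + 1 + 1 = 18. The chapter 13 items repeated at PHD/follow-up are 8 + 2 + 1 + 1 = 12. QSANYPRB is expressly exempt from imputation, and the accessory items in chapter 15 have no # note.

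**Step 2. Is the fill value permitted?** *Used successfully* is not on the value list of any of the 18 items. Nor is it marked NEW under SAP 1.2: in these rows NEW is attached only to labels, where it appears at all.

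**Step 3. Does the rule fire?** For the PSA, implant, connectivity, export and printing blocks the trigger is a real value of the preceding item, so the rule fires. That is 18 − 1 = 17 items at implantation and 12 − 1 = 11 at PHD/follow-up. For battery, the value of PRPRGB is *used successfully*. The Notes cell triggers on *successfully used* and the # note on *Used successfullyyes*. Neither matches, so read literally neither fires and blanks stay missing.

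**Step 4. Size for the items where the rule fires.** Let N be the non-missing answers after filling, n the no-problem answers actually given, and b the filled blanks.

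- No-problem share as written: n/N.
- With the valid fill value: (n + b)/N.
- Difference: b/N.
- Share answering Yes: y/N under both.

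The number b is not in the documents, so the values below are assumptions.

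| N | b = 0 | b = 1 | b = 5 |
|---|---|---|---|
| 50 (planned implantations) | 0 | 1/50 = 2.0 points | 5/50 = 10.0 points |
| 100 (planned PHD/follow-up cases) | 0 | 1/100 = 1.0 point | 5/100 = 5.0 points |

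N is smaller for functions not used in every case. The LV VectorOpt item concerns CRT devices, for which Protocol 8.1.2 plans about 20 implantations and 40 follow-up cases. One filled blank is then worth at least about 1/20 = 5.0 or 1/40 = 2.5 points.

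**Step 5. Battery.** If blanks stay missing, the denominator shrinks. Suppose 50 uses, one reported problem and 10 blanks (all assumed). The problem share is 1/40 = 2.5% without a fill and 1/50 = 2.0% with the fill in the Notes cell.

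**Step 6. Programming listing.** QSPRGAS can be programmed successfully, not programmed successfully, or not done. The trigger *used, but not successfully* is none of these, so that arm of the condition is never true. The listing then depends on QSPRGPRB being a Yes. The any-problem listing at the end of 13.1 also tests QSPRGPRB, not QSPRGAS, and its listed variable is the programmer serial number. A failed programming with QSPRGPRB blank or answered as no problem therefore meets neither condition. It is counted in the QSPRGAS frequency row, but its COPRGAS text is not listed. No frequency changes.

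**The case against.** **The SAP may add report values.** SAP 1.2 allows new nominal values, so the fill could be a deliberate extra category that keeps filled answers apart from given ones. This does not hold: no value is marked NEW, and the battery Notes cell shows that the no-problem answer was meant. The underlying worth of keeping filled and given answers apart does stand. The listings treat unsuccessful use and a noticed problem as separate conditions, so success does not strictly imply that no problem was noticed. The fix therefore includes a count of imputed answers.

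**These are slips that a programmer would correct.** That is likely, but Protocol 11.8 requires any deviation from the valid SAP to be indicated in the reports. It also allows the SAP to be updated before database freeze or closure, which is the cleaner route.

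**The listing gap is narrow.** This stands in large part. It needs a failed programming paired with a blank or no-problem answer, which a data query might resolve. The note in SAP 15.1 reports the programmer serial number for any reported problem and may cover such a case. A failure that is a device deficiency under Protocol 18.3 goes to adjudication and is listed there with its serial number. General comments are also all listed. What remains exposed is the COPRGAS reason text.

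**Stronger readings a reader might infer.**

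- *The fill hides problems or biases the safety result.* Where the rule fires, the Yes share is unchanged and the filled answers appear as their own row. The endpoints come from the adjudication dataset (SAP chapters 10 and 11).
- *It breaches the ban on imputation.* SAP 5.4 bars imputation for the endpoints only.
- *The battery row forces a choice between two rules.* Read literally, neither fires.
- *Protocol 11.2.2 makes the programming listing critical, because it calls problems needing programming adjustments more relevant at follow-up.* That sentence justifies 100 cases for detecting adverse device effects and deficiencies. It is not about this listing. Protocol 7.5 is the relevant text.

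**Conclusion.** Wrong as written, and minor.

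1. Seventeen items at implantation and 11 at PHD/follow-up are filled with a value they do not have. Their no-problem share is understated by b/N, which is zero if there are no blanks after successful use. The problem share does not move.
2. The battery item, the eighteenth at implantation and twelfth at PHD/follow-up, has two inconsistent fill rules with triggers that do not match its values. Taken literally, its blanks stay missing.
3. The programming listing can omit the stated reason for a failed programming, at implantation and at PHD/follow-up, although the failure is still counted.

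The size rests on an assumed b. The counts rest on a literal reading of triggers and fill values, and on taking the cross-reference in SAP 14.1 by its chapter number. The adverse device effect and device deficiency endpoints are unaffected.

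**What to change.** - In all five # notes (12.2; 13.1 implant, data export, printing and battery), set the fill value to the items' own no-problem answer.
- Give the battery Notes cell and its # note that same fill value and the same trigger, *used successfully*.
- Set the QSPRGAS listing trigger to the item's actual failure value, the one for a device not successfully programmed.
- Report the number of imputed answers per item, so that filled answers stay distinguishable from those the investigator gave.

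SAP 14.1 inherits the chapter 13 changes by repetition. The cost is wording in five notes, one cell and one trigger, plus one count per item. No new data or further analyses are needed.
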